## 1 Study Information

### 1.1.1 Study design

This is a randomized, evaluator-blinded, no-treatment controlled study to evaluate the effectiveness and safety of Restylane Volyme for correction of Midface Volume Deficit and/or Midface Contour Deficiency in subjects of Chinese origin, men or women aged 18 years or older.

The study will be conducted at approximately 5 sites located in China, and subjects with a Medicis Midface Volume Scale (MMVS) score of 2, 3 or 4 on each side of the face, as assessed by the Blinded Evaluator, will be enrolled. The subjects will be followed for approximately 14 months.

Only the Evaluator will be blinded, both Treating Investigator and subjects will be aware of the treatment. To avoid inter-observer variability, every effort should be made to ensure that preferably the same individual who made the initial baseline determinations completes all corresponding follow-up evaluations.

For more details regarding the study, and references, please see the Clinical Study Protocol (CSP), MA-33281.

### 1.1.2 Number of subjects and randomization

A total of approximately 168 subjects will be enrolled.

Up to 20 subjects (2 first treated subjects per Treating Investigator, with maximum 2 treating investigators per site) will be enrolled as group A and all subjects in this group will receive treatment with Restylane Volyme. In group B, approximately 148 subjects will be randomized in a **CC1** ratio to treatment with Restylane Volyme or no treatment. The randomization will be stratified by site.

## 1.2 Study Objectives

The study objectives are:

[figure not shown]
- To evaluate the effectiveness of Restylane Volyme in the treatment of Midface Volume Deficit and/or Midface Contour Deficiency.
- To evaluate the safety of Restylane Volyme in the treatment of Midface Volume Deficit and/or Midface Contour Deficiency.

 GALDERMA	<small>Title</small> SAP, 43CH1626, Restylane Volyme Midface	<small>Doc id</small> MA-35135
--	--	--

[figure not shown]
## 1.3 Effectiveness Assessments

### 1.3.1 Medicis Midface Volume Scale (MMVS)

MMVS is a four-point photographic scale that assesses the fullness of the midface from 'Fairly full' (1) to 'Substantial loss of fullness' (4) as described below, see Table 1-1.

The Blinded Evaluator will rate the subject's right and left midface for severity of volume deficiency using the MMVS at screening, baseline, [REDACTED], 6, [REDACTED] months after last treatment in Group A and Treatment Group; and at screening, baseline, [REDACTED] and 6 months after randomization, as well as [REDACTED] and 6 months after last treatment in Control Group. [REDACTED]

Effective date: 2017-11-03 11:43

*Effective*

Version: 1.0

 GALDERMA	<small>Title</small> SAP, 43CH1626, Restylane Volyme Midface	<small>Doc id</small> MA-35135
---	--	--

CCI

## 1.4 Effectiveness Endpoints

### 1.4.1 Primary effectiveness endpoint

The primary effectiveness endpoint is the percentage of responders, defined by at least 1 point improvement from baseline on the MMVS on both sides of the face concurrently, as measured by the Blinded Evaluator at 6 months after last treatment in Treatment Group and 6 months after randomization in Control Group.

CCI

Effective date: 2017-11-03 11:43

**Effective**

Version: 1.0

 GALDERMA	<small>Title</small> SAP, 43CH1626, Restylane Volyme Midface	<small>Doc id</small> MA-35135
CCI		

## 1.5 Safety Assessments

CCI

A two-point scale ('Yes' or 'No') will be used to assess causality of AEs, serious as well as non-serious. The Investigator shall be asked to indicate a response to each of the following questions in the electronic case report form (eCRF):

- *"Do you consider that there is a reasonable possibility that the event may have been caused by the study product?"* and
- *"Do you consider that there is a reasonable possibility that the event may have been caused by the study product injection procedure?"*

If any of these questions are answered with a 'Yes', the AE will be considered related.

 GALDERMA	<small>Title</small> SAP, 43CH1626, Restylane Volyme Midface	<small>Doc id</small> MA-35135
--	--	--

[figure not shown]
Each AE will also be assessed for causal relationship and seriousness by the Sponsor, in order to fulfill regulatory requirements. In case of a disagreement, the AE will be considered '*Related*'.

Any device deficiencies discovered in relation to treatment at baseline and 4-week follow-up visits for the Treatment Group and treatment at 6 months after randomization and 4-week follow-up after 6-moth treatment for the Control Group will be recorded.

## 1.6 Safety Endpoints

Safety endpoints include:

CCI

[figure not shown]

- (ii) Incidence, intensity, duration, and onset of adverse events (AEs) collected throughout the study.

## 2 Statistical Methods

### 2.1 General Methods

CCI

2017-11-03 11:43

Effective date:

## *Effective*

Version: 1.0

## 2.2 Analysis Populations

The following populations for Group B will be defined:

- Safety Includes all subjects in Group B who were treated with Restylane Volyme or randomized to no-treatment group. Subjects are analyzed based on the as treated principle.
- Full Analysis Set (FAS) Includes all subjects in Group B who were treated with Restylane Volyme or randomized to no-treatment group. Subjects are analyzed according to the randomization assignment.
- Per Protocol (PP) Includes all subjects in FAS that comply to the protocol procedures with no deviations that can affect the evaluation of the primary variable.

The FAS population is the primary population for all effectiveness analyses. All safety analyses will be based on the Safety population.

Group A will be followed for safety evaluation throughout the whole study.

### 2.3 Study Subjects

### 2.3.1 *Subject disposition*

The number and percentage of subjects in each study population (FAS, PP, and Safety) will be summarized by site (including subject number) and in total (Table 4-1). Study population variables will also be presented in a data listing.

The disposition of subjects, including reason for withdrawals, will be presented by site and in total (Table 4-4). Number of completed, missed, and withdrawn subjects, as well as subjects continuing in the study will be accounted for by visit and treatment group (Table 4-5 and Table 4-6). Subject accountability will also be presented in a flowchart (Figure 4-1 and Figure 4-2).

All withdrawn subjects will be listed individually, including site number, subject number, treatment group, date of treatment and withdrawal, reason for withdrawal and last visit performed (Table 4-7 and Table 4-8).

Reasons for screening failures will be summarized (Table 4-9).

 GALDERMA	Title SAP, 43CH1626, Restylane Volyme Midface	Doc id MA-35135
--	---	---------------------------

### 2.3.2 *Protocol deviations*

Subjects with CSP deviations will be presented by observed protocol deviation, number of subjects and number of deviations (Table 4-3). Depending on the seriousness of the deviation, the subject might be excluded from the PP population (Table 4-2), which shall be documented prior to database lock (DBL).

Definition of protocol deviations that will exclude subjects from the PP are defined (but not limited to) in Table 2-1 below.

**Table 2-1: Protocol deviations**

Deviation	
GENERAL	
	Visit out-of-window
	* Follow-up at 6 months after last treatment performed earlier than 1 week before the scheduled visit or later than 2 weeks after the scheduled visit in Treatment Group.
	* Follow-up at 6 months after randomization performed earlier than 1 week before the scheduled visit or later than 2 weeks after the scheduled visit in Control Group.
EFFECTIVENESS	
	MMVS assessed by Blinded Evaluator
	* Not done for both sides of the face at 6 months after last treatment in Treatment Group, or at 6 months after randomization in Control Group.
	* Pre-treatment MMVS not available for both sides of the face.
	* More than 1 grade difference in baseline MMVS score between the two sides of the face.
OTHER	
	Inclusion/exclusion criteria
	* Any inclusion criteria affecting primary effectiveness evaluation not met.
	* Any exclusion criteria affecting primary effectiveness evaluation met.

### 2.3.3 *Demographics and Baseline characteristics*

Demographic endpoints and subject baseline characteristics will be presented by treatment group (Table 5-1) using descriptive statistics. Gender, ethnic origin, and baseline MMVS score (assessed by Blinded Evaluator and CCI [REDACTED]) will be summarized as categorical end points using number and percentage of subjects. Age and baseline BMI will be summarized by number of subjects, mean, standard deviation, minimum, median, and maximum values.

 GALDERMA	Title SAP, 43CH1626, Restylane Volyme Midface	Doc id MA-35135
--	--	----------------------------------

### 2.3.4 *Medical history, and concomitant medication and procedures*

All summaries will be based on the Safety population. Concomitant medications will be coded using the World Health Organization (WHO) Drug Dictionary. Medical history will be coded according to medical dictionary for regulatory activities (MedDRA).

#### **Medical history/concurrent disease**

The number and percentage of subjects reporting medical history/concurrent diseases and the number of conditions will be summarized by System Organ Class (SOC) and in total, for all medical history during the whole study and ongoing at study start (Table 5-2 and Table 5-3).

Prior use of facial fillers or implants will be summarized by type of fillers/implants using number and percentage of subjects and number of events (Table 5-4). Prior use of other facial dermatological procedures will be summarized by type of procedure using number and percentage of subjects and number of events (Table 5-5).

#### **Concomitant medication and procedures**

The number and percentage of subjects reporting concomitant medication ongoing at study start, initiated during study and in total (Table 6-1) will be summarized. In addition, the number and percentage of subjects reporting concomitant medication, and the number of medications will be summarized by reason and in total (Table 6-2). Also, the number and percentage of subjects, and the number of medications, will be summarized by ATC code and in total, along with an ATC text description (Table 6-3).

Concomitant medication taken due to an AE will be summarized by ATC code (along with an ATC text description) and in total using number and percentage of subjects and number of medications, and by MedDRA coded AE and whether the AE is related or not (Table 6-4 and Table 6-5).

Concomitant procedures will be presented by reason and in total (Table 6-6), as well as by type of procedure (Table 6-7), using number and percentage of subjects and number of procedures.

### 2.3.5 *Extent of exposure*

Volume injected (mL), for each treatment visit and in total will be presented by treatment group (Table 7-1) using number of subjects, mean, standard deviation, minimum, median, and maximum values. Depth of injection and injection method for each treatment visit will be summarized by treatment group using number and percentage of subjects (Table 7-1).

Local anaesthesia used and post-treatment care for each treatment visit will be summarized by treatment group using number and percentage of subjects (Table 7-2).

 GALDERMA	Title SAP, 43CH1626, Restylane Volyme Midface	Doc id MA-35135
--	---	---------------------------

### 2.3.6 Post-treatment examinations

Change from baseline in post-treatment BMI will be presented for subjects with a change in BMI  $\geq 2$  units, if applicable (Table 8-1).

## 2.4 Effectiveness Analysis

### 2.4.1 Data sets analyzed

All effectiveness variables will be analyzed using the FAS population. The primary analysis will be repeated using the PP population. If it is deemed necessary, other analyses will be repeated using the PP population.

### 2.4.2 Handling of missing data

[figure not shown]
Number of missing values will be summarized and reported as appropriate.

Different assumptions regarding the missing data will be used. For the primary effectiveness analysis, missing values in the FAS will be assumed to be missing due to lack of effect. Therefore missing data up to the Month 6 visit will be imputed using the baseline observation carried forward (BOCF) method. As an alternative approach, missing data will be assumed to be unrelated to treatment effect. To impute data under this assumption, missing data up to the Month 6 visit will be imputed using the hot deck method (Table 9-2). Both of these alternatives will estimate the effectiveness of the treatment policy (irrespective of use of disallowed treatments, procedures, or medications) rather than the true, clinical treatment effect.

To obtain an estimate of the true, clinical treatment effect, the primary effectiveness analysis will be performed using the PP population.

All other endpoints will be analyzed on available data, i.e. no imputations will be done.

[figure not shown]
CCI

[figure not shown]
 GALDERMA	Title SAP, 43CH1626, Restylane Volyme Midface	Doc id MA-35135
--	--	---------------------------

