10.6 Handling of Missing Data

Number of missing values will be summarized and reported as appropriate.

Different assumptions regarding the missing data will be used. For the primary effectiveness analysis, missing values in the FAS will be assumed to be missing due to lack of effect. Therefore missing data up to the Month 6 visit will be imputed using the baseline observation carried forward (BOCF) method. As an alternative approach, missing data will be assumed to be unrelated to treatment effect. To impute data under this assumption, missing data up to the Month 6 visit will be imputed using the hot deck method. More details will be given in the SAP. Both of these alternatives will estimate the effectiveness of the treatment policy (irrespective of use of unallowed treatments, procedures, or medications) rather than the true, clinical treatment effect.

To obtain an estimate of the true, clinical treatment effect, the primary effectiveness analysis will be performed using the PP.

All other endpoints will be analysed on available data, i.e. no imputations will be done.

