**Table 4-5: Subject accountability by visit: subjects randomized to treatment with Restylane Volyme, Group B**

Visit	Number of subjects			
	Completed	Missed	Withdrawals	Continuing in study
Baseline/initial treatment				
4W follow-up/optional touch-up				
4W follow-up after last treatment				
3M after last treatment				
6M after last treatment				
9M after last treatment				
12M after last treatment				

[figure not shown]
 GALDERMA	Title SAP, 43CH1626, Restylane Volyme Midface	Doc id MA-35135
---	---	---------------------------

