**Table 4-6: Subject accountability by visit: subjects randomized to no-treatment control, group B**

Visit	Number of subjects			
	Completed	Missed	Withdrawals	Continuing in study
Baseline				
4W follow-up				
3M follow-up				
6M follow-up/treatment				
4W follow-up/optional touch-up				
4W follow-up after last treatment				
3M after last treatment				
6M after last treatment				

2017-11-03 11:43

Effective date:

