**Table 4-8: Withdrawn subjects, Group B**

Treatment group	Site	Subject number	Date of treatment		Last visit performed	Date of withdrawal	Reason for withdrawal
			Initial treatment	Optional touch-up treatment			
Restylane Volyme							
Control							

 GALDERMA	<small>Title</small> SAP, 43CH1626, Restylane Volyme Midface	<small>Doc id</small> MA-35135
--	--	--

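### Does scoring every missing untreated control as a non-responder call for a further sensitivity analysis?

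*SAP*

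**What the plan says.** SAP 2.4.2 sets the primary assumption: "For the primary effectiveness analysis, missing values in the FAS will be assumed to be missing due to lack of effect". Protocol 10.6 draws the consequence in the same terms: "Therefore missing data up to the Month 6 visit will be imputed using the baseline observation carried forward (BOCF) method". Neither section distinguishes the arms, and footnote 1 of SAP Table 9-1 repeats the rule for the full analysis set (FAS). SAP 2.4.3 defines a responder as improving by one point or more on both sides together.

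Two other analyses are readable. One is a hot-deck imputation, which assumes missingness is unrelated to treatment effect. The other is the per-protocol (PP) analysis, which by footnote 2 of Table 9-1 uses complete data without imputation. SAP 2.4.2 says that both imputations target a treatment-policy effect, whether or not prohibited treatments were used.

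On reporting, SAP 2.4.2 opens by promising a summary of missing values. Tables 4-5 and 4-6 count missed visits and withdrawals by visit, one table per arm. Withdrawn subjects are listed by arm in "Table 4-8: Withdrawn subjects, Group B". SAP Table 2-1 makes an absent Month 6 blinded score a reason for PP exclusion, and Table 4-2 lists exclusions by reason with subject numbers.

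**The concern.** Lack of effect cannot explain missingness in an arm that has received nothing. SAP 2.7 allows controls a response rate of up to 35%, yet a carried-forward baseline gives missing controls 0%. If controls are lost more often than treated subjects, the control rate is pushed down and the difference up.

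The controls know they are untreated (protocol 4.4.2) and enrolled because they wanted augmentation (protocol 5.2), so heavier loss among them is conceivable. One who left and was treated elsewhere might really have improved by Month 6. Under a treatment-policy aim that improvement would count. Baseline carried forward scores a failure, a hot deck borrows someone else's score, and the PP analysis drops the subject. With 37 controls, a few such subjects could decide significance if the true effect is smaller than planned. A tipping-point table by arm is the usual way to show this, and none appears in the readable text.

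**Working it through.** **Inputs from the documents.** 111 treated and 37 control subjects (protocol synopsis; together 148). Response rates of 70% and at most 35% (SAP 2.7).

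**Assumptions.** Two-sided 0.05, Fisher's exact or uncorrected chi-square test, and the missing fractions; none of these is readable. Write mT and mC for the fractions missing in the treatment and control arms. Alpha, power and dropout are redacted, so 148 cannot be reproduced uniquely.

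**Step 1: direction of the bias.** With missingness unrelated to outcome within arm, the expected difference at planned rates is 0.70(1−mT) − 0.35(1−mC).
- 5%/5%: 66.5 − 33.25 = 33.25 points
- 10%/10%: 63.0 − 31.5 = 31.5 points
- 5%/10%: 66.5 − 31.5 = 35.0 points
- 5%/20%: 66.5 − 28.0 = 38.5 points

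It exceeds 35 points only if 0.35·mC > 0.70·mT, that is mC > 2·mT. With a common response rate p the bias is p(mC − mT), positive only if mC > mT. At p = 0.35 and 5%/20% it is 0.35 × 0.15 = 5.25 points.

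**Step 2: false-win rate.** This is the exact probability of p < 0.05 favouring treatment when both arms share response rate p. Responder counts are binomial with rates p(1−mT) and p(1−mC).

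| p | mT/mC | Fisher | chi-square |
|---|---|---|---|
| 0.35 | none | 2.1% | 2.3% |
| 0.35 | 10%/10% | 2.0% | 2.3% |
| 0.35 | 15%/5% | 0.7% | 0.8% |
| 0.35 | 5%/15% | 4.9% | 5.3% |
| 0.35 | 5%/20% | 7.2% | 7.8% |
| 0.20 | 5%/20% | 4.0% | 4.8% |
| 0.10 | 5%/20% | 2.2% | 2.8% |

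Inflation needs clearly control-heavy loss and a control rate near the plan's maximum. These figures also assume that missing subjects resemble observed ones in their own arm. That is the case the PP analysis addresses, as does a hot deck with same-arm donors.

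**Step 3: tipping.** Treated responders are held at the baseline-carried-forward count, and missing controls are switched to responders.

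| Treated | Control | Fisher p | chi-square p |
|---|---|---|---|
| 74/111 (5% missing) | 12/37 | 0.0004 | 0.0003 |
| 74/111 | 14/37 (both missing respond) | 0.003 | 0.002 |
| 70/111 (10% missing) | 12/37 | 0.002 | 0.001 |
| 70/111 | 14/37 (two of four) | 0.012 | 0.007 |
| 70/111 | 16/37 (four of four) | 0.053 | 0.034 |
| 60/111 | 12/37 | 0.024 | 0.023 |
| 60/111 | 13/37 (one) | 0.058 | 0.046 |
| 60/111 | 14/37 (two) | 0.128 | 0.088 |

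At 5% missing, the most extreme scoring stays significant. At 10%, losing significance takes all four missing controls, and only under Fisher. At a 35% rate, four of four has probability 0.35^4 = 1.5%. The 60/111 rows start close to the threshold; with 70% response and 10% of treated subjects missing (rate 0.63), 60 or fewer treated responders has probability about 3%.

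**Step 4: can the gap be shown?** The hot-deck donor pool is unreadable. At 10% missing per arm, 100 treated and 33 controls are observed. Donors pooled across arms would respond at (100 × 0.70 + 33 × 0.35)/133 = 81.55/133 = 61%, well above 35%. Text after SAP 2.4.2 and 2.4.3 is redacted, as is Table 9-2. So it cannot be said that the plan lacks an analysis in which missing controls outperform observed ones.

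**The case for a change.** The strongest case for a change is that the assumption is wrong in principle for an untreated arm, the arm is small, and a tipping-point table costs one paragraph and no new data. If pre-specified before database lock, it could not later look data-driven. Tables 4-5 and 4-6 count missed visits and withdrawals, but do not show whether the primary p-value depends on how missing controls were scored. With heavier loss the dependence is real: at 20% missing per arm, 62/111 against 10/37 gives Fisher p = 0.003, and crediting about half the missing controls (14/37) gives 0.087.

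What stands is that the stated rationale does not fit controls, and that such a table would be informative if loss proved heavy. The route to harm is narrow, however. Protocol 4.6 keeps subjects who use a prohibited procedure in scheduled follow-up, so their real scores are collected. Protocol 5.5 asks for a termination visit where possible, and the control schedule includes a blinded rating at that visit. Controls are offered treatment at Month 6 (protocol 4.1), which is a reason to stay, and protocol 2.5 says no midface filler was available in China. Treated subjects who have a touch-up reach their primary visit about four weeks later than controls, so the schedule gives no reason to expect control-heavy loss. Unscored ratings at attended visits would surface through Tables 2-1 and 4-2; only a split by arm is not explicit.

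**Conclusion.** No change is needed. Baseline carried forward does score every missing control as a failure, but it does the same to treated subjects. It is conservative or neutral at equal missingness, and favours treatment only if control loss exceeds treated loss (no true effect) or is more than twice it (70% against 35%). The 7–8% false-win rate needs 5%/20% missing and a 35% common rate, and the plan already pairs the primary analysis with ones that address that pattern. The remaining scenario is controls who leave and then do better than those who stay. The protocol's follow-up rules limit it, and its absence from the plan cannot be shown through the redactions. A descriptive tipping-point table would be a reasonable extra if loss turns out heavy; it would correct no error and would not alter the primary analysis or the success criterion.

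This rests on assumed two-sided 0.05, an assumed Fisher or chi-square test, and assumed missing rates. It also relies on hot-deck donors coming from the same arm, or on the PP analysis alone, to cover unequal loss unrelated to outcome.

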#### 2.4.3 Primary analysis

[figure not shown]
The percentage of responders (a responder will be defined as a subject with at least 1 point improvement from baseline MMVS on both sides of the face concurrently) will be calculated for each group at Month 6 (after last treatment for Treatment group, and after randomization for Control group) based on the Blinded Evaluator's assessment. **CCI**

